**Table 11. RECIST and GCIG CA-125 Criteria**

RECIST Response	GCIG CA-125 Response	RECIST + GCIG CA-125 Combined
CR (requires normalization of CA-125)	CA-125 within normal range	Response
PR	Response	Response
PR	No Response	Response
SD	Response	Response
SD	No Response	No Response
PD	Response	No Response
PD	No Response	No Response

Abbreviations: CA-125 = cancer antigen 125; CR = complete response; GCIG = Gynecologic Cancer InterGroup; PD = progressive disease; PR = partial response; RECIST = Response Evaluation Criteria in Solid Tumors; SD = stable disease

The response rate will be summarized with frequencies and percentages in addition to 95% CI of the proportion using Clopper-Pearson methodology.

#### 9.6.2.2 ORR by RECIST v1.1 as Assessed by the Investigator and GCIG CA-125 Response According to Molecularly-defined HRD Subgroups

All patients in Cohort A1 will have a centralized tumor tissue test and the results from the NGS test will be utilized to divide the patients into the following molecularly-defined HRD subgroups:

- **Non-tBRCA LOH+:** Patients who are found to not have a BRCA mutation in their tumor, but where the percent of LOH is  $\geq 16\%$  (ie, BRCAwt/LOHhigh);
- **Non-tBRCA LOH-:** Patients who are found to not have a BRCA mutation in their tumor, but where the percent of LOH is  $< 16\%$  (ie, BRCAwt/LOHlow);
- **Non-tBRCA Unknown:** Patients who are found to not have a BRCA mutation in their tumor, but where the percent of LOH is unknown due to missing results and/or failed test result(s) (ie, BRCAwt/LOHunknown); or
- **sBRCA (somatic tBRCA):** Patients who are found to have a BRCA mutation in their tumor but not in their blood sample.

The analyses of the response rates for each of these HRD subgroups will be performed as described in [Section 9.6.2.1](#). In addition, different cut-off of LOH may be explored.

#### 9.6.2.3 Progression-free Survival (PFS)

Progression-free survival as assessed by investigator by RECIST is defined as the time from first dose to disease progression, according to RECIST v1.1 criteria as assessed by investigator, or death due to any cause, whichever occurs first. PFS will be calculated as 1+ the number of days from the first dose of study treatment to first occurrence of disease progression (per RECIST v1.1) or death due to any cause, whichever occurs first. For patients who continue treatment post-progression, the first date of progression (per RECIST v1.1) will be used for the analysis. Patients without a documented event of progression will be censored on the date of their last adequate tumor assessment (ie, radiologic assessment) or date of first dose of study treatment if no post-baseline tumor assessments have been performed. Only tumor scans prior to start of any subsequent anticancer treatment are included.

The Kaplan-Meier methodology will be used to summarize PFS. If able to be estimated, the 50th percentile (median) together with a 95% CI, will be presented based on log-log transformation. The number of patients with events and the number of censored patients will also be presented.

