### 2.2 Secondary Objectives

The secondary objectives of this study, using the same comparisons as the primary objective, are:

- To evaluate the ORR by RECIST v1.1 and Gynecologic Cancer InterGroup (GCIG) cancer antigen 125 (CA-125) criteria (*Cohort A1 only*)
- To evaluate the ORR by RECIST v1.1 as assessed by the investigator, according to molecularly-defined HRD subgroups: BRCAwt/LOHhigh; BRCAwt/LOHlow; BRCAwt/LOHunknown; and sBRCA (*Cohort A1 only*)
- To estimate PFS (*Cohort A1 only*)
- To evaluate DOR (*Cohort A1 only*)
- To evaluate safety and tolerability of rucaparib in combination with nivolumab

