p = Includes dipstick for protein, glucose, blood, pH, and ketones. If dipstick findings abnormal, perform microscopic evaluation. To be conducted at screening only, but may be conducted at other times as clinically indicated.

q = Disease assessment to include clinical examination and appropriate imaging techniques, including CT scans of the chest, abdomen, and pelvis, with appropriate slice thickness per RECIST; other assessments (MRI, X-ray, PET, and ultrasound) may be performed if required. The same methods used to detect lesions at baseline are to be used to follow the same lesions throughout the clinical study. If a patient has known brain metastases, this disease should be evaluated at each required assessment. Copies of CT scans will be collected from all patients. Independent radiology review may be conducted on all or a subset of CT scans.

r = Tumor scans to be performed at the end of every 8 calendar weeks (±7 days) during the Treatment Phase, from the start of the oral/IV combination treatment on Cycle 2 Day 1. A confirmatory scan should be performed ≥ 4 weeks after an initial response of PR or CR is observed. Patients who have been on study at

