**Table 6. Study CO-338-097 Schedule of Assessments**

	Screening Phase	Treatment Phase a (±3 days of scheduled timepoint)						Post-treatment Phase			
		Cycle 1			Cycle 2		Cycle 3+	EOT	FU-28 28 ±3 d after last oral/IV dose	FU-100 100 +7 d after last IV dose	LTFU
Procedure	D-28 to D-1 b	D1 c,d	D15 e	D28	D1 d	D15 d	D1 d				

least 18 months, may decrease the frequency of disease assessments to every 12 calendar weeks (±7 days). Tumor assessments should continue as per protocol even if dosing is delayed.

- s = Disease assessments should also be done at the time of treatment discontinuation if it has been ≥ 8 weeks since the last assessment.
  - t = If treatment was discontinued for reasons other than radiologic disease progression or death, radiologic tumor assessment (using the same methodology as was used at initial study screening) will continue until confirmed radiographic disease progression, death, or initiation of subsequent treatment. Assessment at 12-week (±7days) intervals from Cycle 4 Day 1 for the first 18 months after initiation of study treatment, and every 24 weeks (±14 days) thereafter, until objective radiological disease progression by RECIST v1.1, as assessed by the investigator, is documented.
  - u = A mandatory biopsy or resection of tumor tissue must be collected ≤ 42 days prior to first dose of rucaparib. Alternatively, tumor tissue collected > 42 days prior to the first dose of rucaparib may be submitted, provided there have been no intervening anticancer treatments during this period and the tissue is of adequate quality. Tumor tissue samples should be from primary or metastatic tissue. Patients may be enrolled prior to tumor tissue being analyzed by the central laboratory, provided there is confirmation that the tumor tissue has been received by the central laboratory
- Tumor tissue must be obtained from a soft tissue tumor lesion; ascites is not acceptable. Refer to the Laboratory Manual for detailed sample handling instructions.

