#### 7.4.8 Long-term Follow-up

Patients who complete the Safety Follow-up Visit(s) after the last dose of study treatment will continue in long-term follow-up as described below.

- Disease assessment for patients who discontinued treatment for reason other than disease progression or death. Tumor scans should continue to be performed at 12-week ( $\pm 7$  days) intervals for the first 18 months after initiation of study treatment, and every 24 weeks ( $\pm 14$  days) thereafter, until radiologic disease progression by RECIST v1.1, as assessed by the investigator, is documented.
- CA-125 measurement (Local) may be performed at the same time as radiological imaging, at the discretion of the investigator.
- Subsequent treatments, secondary malignancy monitoring, and overall survival information will be collected for all patients every 12 weeks ( $\pm 14$  days) until death, loss to follow-up, withdrawal of consent from study, or closure of the study. Follow-up can be performed via the telephone. Diagnosis of any secondary malignancy requires appropriate documentation (ie, laboratory and/or pathology reports) and should be reported as indicated in [Section 8.10](#).
- SAEs related to study drug and all AESIs, irrespective of causality, are to be reported as specified in [Section 8.10](#).

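### PFS cuts scans but not deaths at next-line therapy, so whether a patient who switches without progression is censored depends on whether she later dies

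*Combined protocol and SAP*

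**What the plan says.** PFS in Cohort A1 is a secondary objective (Section 2.2). Section 9.6.2.3 sets the following rules:

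- **Event:** "first occurrence of disease progression (per RECIST v1.1) or death due to any cause, whichever occurs first". No limit is placed on deaths after new therapy.
- **Scans:** "Only tumor scans prior to start of any subsequent anticancer treatment are included".
- **Censoring:** "Patients without a documented event of progression will be censored on the date of their last adequate tumor assessment", or at first dose if there is no post-baseline scan.
- **Estimator:** "The Kaplan-Meier methodology will be used to summarize PFS".

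Section 7.4.8 says that "overall survival information will be collected for all patients every 12 weeks", so deaths after a switch will be in the database. Scans mostly will not: under Table 6, footnote t, imaging after stopping treatment without progression "will continue until confirmed radiographic disease progression, death, or initiation of subsequent treatment". The Synopsis (Efficacy Assessments) and Section 7.5.3.1 also stop imaging at new therapy. The Synopsis (Post-Treatment Follow-up Phase) and Sections 3.1.4 and 7.4.8 state no such stop.

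Section 9.1 leaves further detail to the SAP. The supplied document contains no SAP text on deaths after new therapy.

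**The concern.** The two components of PFS are treated differently once new therapy starts: progression stops counting and death does not. For a patient who switches without progression, follow-up after the switch enters the curve only if she goes on to die before cut-off. If she survives, that same period is removed by back-dating her censoring to the last scan before the switch. Kaplan-Meier needs censoring that carries no information about what comes next, and here the later outcome itself decides who is censored.

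Separately, the censoring sentence mentions progression and not death. Taken literally, it censors a patient who dies without progression. If she dies before her first post-baseline scan, it censors her at first dose. That contradicts the event definition in the same section, and two programmers could produce different curves from this text.

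Switching without progression is foreseeable. Section 3.2 ends treatment for safety risk, intercurrent illness and noncompliance; Table 4 requires discontinuation for several toxicities; and Appendix 1 recognises symptomatic deterioration without objective progression. With at most 43 patients, a few such cases can move the curve.

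**Working it through.** **No plan figure to reproduce.** The documents state no median PFS, PFS event count or switching rate. Their sample-size figures concern ORR and do not enter here.

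**Step 1: one patient, three outcomes.** Take ten patients. Nine progress at months 2, 3, 4, 5, 7, 8, 9, 11 and 14. The tenth has her last scan at 5.5 months and then switches without progression. After the events at 2, 3, 4 and 5 months, S = 6/10 = 0.60. Then, under Section 9.6.2.3 with deaths counted:

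| Tenth patient | Treatment in the analysis | S at 10 months |
|---|---|---|
| Alive at cut-off | censored at 5.5 | 0.60 × 4/5 × 3/4 × 2/3 = 0.24 |
| Dies at month 20 | at risk to 20, event | 0.60 × 5/6 × 4/5 × 3/4 = 0.30 |
| Dies at month 6.5 | event at 6.5 | 0.60 × 5/6 × 4/5 × 3/4 × 2/3 = 0.20 |

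Her history up to 5.5 months is the same in each row. Only the later death changes the estimate, and it can move it either way.

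**Step 2: the literal censoring sentence.** Nivolumab starts at Cycle 2 Day 1 (day 29), and the first on-treatment scan comes 8 weeks later, at Cycle 4 Day 1: 29 + 56 = day 85, about week 12. A death before then with no scan is an event under the definition but is censored at first dose under the censoring sentence.

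**Step 3: illustrative size.** All inputs are assumptions: median PFS 6 months, exponential; a constant switching hazard, unrelated to imminent progression; progression hazard unchanged by the switch; median survival after progression 18 months; cut-off 36 months. The true values are then 6.0 months and 25% at 12 months. Large-sample Kaplan-Meier results for the rule as written, with deaths counted, are:

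| Switching before progression | Median (months) | 12-month PFS |
|---|---|---|
| 7% | 6.1 | 26% |
| 20% | 6.4 | 29% |
| 27% | 6.6 | 31% |

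In this setting, cutting both scans and deaths at the switch returns 6.0 months and 25%.

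**Step 4: is the direction fixed?** A grid of 144 assumed scenarios was run: switching 10–30%, median PFS 5 or 8 months, median survival after switch or progression 3, 12 or 24 months, cut-off 18 or 36 months, and progression hazard after the switch 0.3 to 2 times the earlier hazard. The shift in the median under the rule as written, against counting every progression and death, was:

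| Progression hazard after switch | Shift in median (months) |
|---|---|
| 2 times | +0.16 to +1.27 |
| unchanged | +0.07 to +0.74 |
| 0.5 times | −0.23 to +0.37 |
| 0.3 times | −0.51 to +0.16 |

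Against censoring at the switch and ignoring later deaths, the shift ran from about −1.1 to +0.4 months and was positive in about half of the scenarios.

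**Step 5: does cutting both remove the bias?** Not if patients switch because progression is near. Suppose 20% switch at 90% of their time to progression, with the true values again 6.0 months and 25%. With 18-month median survival after the switch, the rule as written gives about 7.6 months and 34%, and cutting both gives about 7.4 and 32%. With 6-month survival, the figures are about 7.25 months and 31% as written, against 7.4 and 32%.

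**The case against.** The strongest reply has four parts.

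1. **The size is small and assumed.** This is correct. At 7% switching the shift is about 0.1 month and 1 point. With 43 patients the standard error of a 25% rate is √(0.25 × 0.75 / 43) = 6.6 points, larger than the 4-point shift at 20% switching. The plan also limits switching without progression, since a CA-125 rise not confirmed radiologically does not end treatment and scans continue after discontinuation. This bounds the importance of the point. It does not supply the missing rule.

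2. **The direction is not established.** A reader might infer that the rule inflates PFS. The documents do not support that as a certainty: they give neither switching nor post-switch rates, and Step 4 shows that the sign can reverse when next-line therapy delays progression. Step 1 shows that early deaths after a switch lower the curve.

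3. **The censoring sentence is only loose wording.** This is plausible, because the section states twice that death is an event. A reader might conclude that the plan intends to delete deaths without progression; the event definition says otherwise. What stands is that the two sentences conflict and need to agree.

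4. **Cutting both at new therapy has its own bias.** Step 5 confirms this. The change removes dependence on later death, but it does not guarantee an unbiased PFS.

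**Conclusion.** The point holds as a defect of definition. With deaths counted, Section 9.6.2.3 makes censoring depend on the future for every patient who switches without progression; this follows from the text and needs no assumption. Its censoring sentence also conflicts with its event definition. The size does rest on assumptions: under those of Step 3, about 0.4 month and 4 points at 20% switching, and about 0.1 month and 1 point at 7%. The direction is often upward but not fixed.

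The consequence is limited. PFS is a secondary, descriptive, single-cohort estimate, and the ORR decision does not use it. The rule should still be settled before the data are seen, because otherwise an unstated programming choice determines the curve. Duration of response (Section 9.6.2.4) has the same scan cut but does not count death, so this asymmetry does not arise there.

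**What to change.** 1. In the censoring sentence of Section 9.6.2.3, refer to patients without documented progression **or death**.
2. Apply the existing cut to both components. Suggested text: *A PFS event is RECIST progression or death from any cause, if it occurs before subsequent anticancer treatment begins. A patient with neither is censored at her last adequate scan before that treatment, or at first dose if she has none. Death before the first post-baseline scan is an event.*
3. Report the number of patients censored for new therapy, and say that this censoring may be informative if patients switch because progression is imminent.
4. Optionally, add a sensitivity analysis counting all available progressions and deaths regardless of new therapy, labelled as limited to the scans available. The imaging passages listed above, some of which stop scans at new therapy and some of which do not, should be reconciled.

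Items 1 to 3 cost only wording and one reported count. Item 4 costs one table; making it complete would require imaging to continue after new therapy. If a separate SAP already settles the rule, the protocol should be made to match it.

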#### 9.6.2.4 Duration of Confirmed Response (DOR)

Duration of response (DOR) for any confirmed RECIST CR or PR will be measured from the date of the first response until the first date that PD is documented. DOR will be summarized as a time to event variable. For patients who continue treatment post-progression, the first date of progression (per RECIST v1.1) will be used for the analysis. Any patients with an ongoing response will be

censored on the date of their last adequate tumor assessment (ie, radiologic assessment) or date of first dose of study treatment if no post-baseline tumor assessments have been performed. Only tumor scans prior to start of any subsequent anticancer treatment are included.

The Kaplan-Meier methodology will be used to summarize DOR. If able to be estimated, the 50th (median) together with a 95% CI, will be presented. The number of patients with events and the number of censored patients will also be presented

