## 9 PLANNED STATISTICAL METHODS

### 9.1 General Considerations

All safety analyses will be summarized for all patients who received at least 1 full or partial dose of protocol-specified treatment. Efficacy will be summarized for all treated patients according to the intent-to-treat principle. Cohorts A1 and A2 will be summarized separately for all safety and efficacy analyses.

Quantitative variables will typically be summarized using frequencies and percentages for appropriate categorizations and may also be summarized using descriptive statistics. For variables summarized with descriptive statistics, the following will be presented: N, mean, standard deviation (StD), median, minimum, and maximum. Categorical variables will be presented using frequencies and percentages.

The Kaplan-Meier methodology will be used to summarize time-to-event variables. If estimable, median (50th percentile) with the 95% confidence interval (CI) will be summarized. The number of patients with events and the number of censored patients will also be presented.

All data will be used to their maximum possible extent but without any imputations for missing data. Unless otherwise specified, baseline is defined as the last measurement on or prior to the first day of study drug administration.

All statistical analyses will be conducted with the statistical analysis software (SAS®) System, Version 9.3 or higher. Further details around the statistical analyses planned in this study will be outlined in the Statistical Analysis Plan (SAP).

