### Duration of Overall Response

The duration of overall response is measured from the time measurement criteria are met for CR or PR (whichever is first recorded) until the first date that recurrent or PD is objectively documented (taking as reference for PD the smallest measurements recorded since the treatment started).

The duration of overall CR is measured from the time measurement criteria are first met for CR until the first date that recurrent disease is objectively documented.

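### DOR ends only at documented progression and leaves a responder's death without progression to be censored, which tends to lengthen the reported duration (minor)

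*Combined protocol and SAP*

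**What the plan says.** Section 9.6.2.4 defines DOR for confirmed RECIST responders: it "will be measured from the date of the first response until the first date that PD is documented". Death is not mentioned. The section's one censoring rule opens with "Any patients with an ongoing response will be" and assigns those patients the date of their last adequate scan. It adds: "Only tumor scans prior to start of any subsequent anticancer treatment are included". DOR is then summarised by Kaplan-Meier with a median and 95% CI.

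Appendix 1, under Duration of Overall Response, gives a matching end point: "until the first date that recurrent or PD is objectively documented".

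Section 9.6.2.3 treats PFS differently. The event is progression "or death due to any cause, whichever occurs first", and the section says this twice. Its censoring sentence is looser: "Patients without a documented event of progression will be censored on the date of their last adequate tumor assessment".

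DOR is a secondary objective in Cohort A1 and exploratory in Cohort A2 (Sections 2.2 and 2.3). Section 9.1 leaves further analysis detail to the SAP. Nothing in the text supplied adds death to the DOR definition.

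**The concern.** Take a responder who dies before any scan shows progression. That death is a PFS event but not a DOR event, and no reason is given for the difference. Because PD is the only DOR event and the last adequate scan is the only censoring date for a responder, the patient can enter the Kaplan-Meier analysis only as censored, together with patients whose response continues. That censoring is informative, because the response did not outlast the patient.

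The situation is plausible. Patients who stop treatment without progression are scanned at 12-week intervals and later at 24-week intervals (Section 7.4.8). Appendix 1 itself foresees deterioration without objective evidence of progression.

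The omission looks more like carried-over wording than a choice. The DOR censoring rule falls back on the date of first dose for patients with no post-baseline scan, and a confirmed responder cannot be such a patient.

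At stake is how durable the responses look in a single-arm study. The bias tends to be favourable, and the confidence interval does not reflect it.

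**Working it through.** **The plan's own figures.** There is no planned figure for DOR. The only design figure is the Simon design for ORR (Section 9.2.1). It reproduces: stopping at 2/18 or fewer and requiring more than 7/43 at the end (the 7 comes from a search, as the plan does not state it) gives type I error 0.0480 at ORR 10% and power 0.8003 at ORR 25%. None of this depends on DOR.

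**Inputs.**
- Responders: 43 × 0.25 = 10.75, taken as 11 (Section 9.2.1).
- Illustrative medians: 11.3 and 5.8 months, from the LOH+ and LOH- groups without a tumour BRCA mutation in Table 1. They are anchors only. They come from rucaparib alone, and the table does not say whether death counted.
- f, the share of response endings that are deaths without documented PD: not in the documents. Assumed 5%, 10% and 20%.
- Follow-up: 24 months, assumed.

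**1. Effect on the median.** Let the total hazard of PD or death be λ, constant, with PD hazard (1 − f)λ. Counting both events, the median is ln 2/λ. Censoring deaths, Kaplan-Meier estimates exp(−(1 − f)λt), with median ln 2/((1 − f)λ). The ratio is 1/(1 − f).

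| f | ratio | 5.8 months becomes | 11.3 months becomes | 12-month estimate at 11.3 (47.9% with deaths counted) |
|---|---|---|---|---|
| 5% | 1/0.95 = 1.05 | 6.1 | 11.9 | 49.7% |
| 10% | 1/0.90 = 1.11 | 6.4 | 12.6 | 51.6% |
| 20% | 1/0.80 = 1.25 | 7.25 | 14.1 | 55.5% |

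The last column is 0.5^(12(1 − f)/11.3). At f = 0 the two definitions agree.

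**2. Chance that it arises at all.** The share of responses ended by 24 months is q = 1 − 0.5^(24/median): 0.771 for 11.3 months and 0.943 for 5.8 months. P(at least one such death) = 1 − (1 − fq)^11.
- Median 11.3: 35%, 59%, 84% for f = 5%, 10%, 20%.
- Median 5.8: 41%, 66%, 90%.

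**3. Scan dates and small numbers.** Table 6, footnote r, reads: "Tumor scans to be performed at the end of every 8 calendar weeks (±7 days) during the Treatment Phase". A simulation used that interval with uniform ±7-day jitter, 11 responders, 24 months of follow-up and 20,000 trials per setting. The PD-only median was longer than the PD-or-death median in 16.7%, 31.4% and 56.5% of trials (true median 5.8) and in 18.5%, 34.4% and 58.6% (true median 11.3), for f = 5%, 10% and 20%. It was shorter in no more than 31 of 20,000 trials in any setting. A reversal can occur because censoring goes back to the last scan. With PD at weeks 9 and 16 and a death at week 20 last scanned at week 8, the PD-or-death median is week 16 and the PD-only median is week 9. Medians also snap to scan dates, so at f = 5% or 10% the typical median moved little at these two anchors.

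**4. Sampling error.** Expected events are 11 × 0.771 = 8.5 (median 11.3) and 11 × 0.943 = 10.4 (median 5.8). An approximate 95% factor is exp(±1.96/√events): 0.51 to 1.96, and 0.54 to 1.84. Both are wider than the largest ratio in step 1.

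**The case against.** The strongest reply is that the text is silent and does not state a plan to count the dead as ongoing responders. Section 9.6.2.4 censors patients with an ongoing response, and a patient who has died has none. That stands as a matter of wording: a reader might infer that the plan expressly censors deaths, and it does not. It still leaves no other place for such a patient in the analysis, so the definition needs repair on either reading.

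Next, a PD-only duration agrees with Appendix 1, which summarises RECIST, and DOR need not share its events with PFS. That is also fair. A PD-only DOR can be a deliberate choice, but then it should be stated and the deaths shown.

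Third, the SAP may settle the matter. It may, but no text supplied does so, and a SAP that counted death would depart from the event rule in Section 9.6.2.4.

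A reader might also infer from the loose PFS censoring sentence that PFS deaths are censored. The documents do not support that, because the same section names death as an event twice. Only the wording needs aligning.

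Finally, one could compute 1 − (1 − f)^11 = 43%, 69% and 91% for the chance of such a death. That assumes every response ends within follow-up, which overstates the chance. Step 2 of the working allows for 24 months.

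**Conclusion.** The point holds as a minor one. Documented PD or recurrence is the only DOR event, death without PD is not addressed, and the only available handling tends to lengthen the reported DOR. Under constant hazards the median is inflated by 5%, 11% or 25% for f of 5%, 10% or 20%. Those values of f are assumptions, and the effect is zero if no responder dies without documented PD. In a single trial of about 11 responders the median may not move, and sampling error exceeds the shift.

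A reader might infer that the trial's efficacy conclusion is at risk. It is not: the decision rule rests on ORR (Sections 9.2.1 and 9.10), and DOR is descriptive with no test or threshold.

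**What to change.** In Section 9.6.2.4, define DOR as the time from first documentation of a subsequently confirmed CR or PR to first RECIST v1.1 PD or death from any cause, whichever is earlier. Censor responders with neither event at their last adequate scan. Censor those who start subsequent anticancer therapy first at the last adequate scan before it, because the present text restricts scans but says nothing about later deaths.

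State how a death after missed scans is treated, using the same rule for DOR and PFS. Otherwise a responder who stops scanning and dies much later would contribute a long response that ends at death.

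In Appendix 1, say that Section 9.6.2.4 governs the analysis. In Section 9.6.2.3, reword the censoring sentence to cover patients without documented progression or death. Carry the definition into the SAP and the Cohort A2 analysis (Section 9.6.3). Report the number of responders who die without documented PD. PD-only DOR can stay as a sensitivity analysis.

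The cost is small. Survival and subsequent treatments are already collected every 12 weeks (Sections 3.1.4 and 7.4.8). The protocol wording needs an amendment with IEC/IRB approval (Section 10.7) and can wait for the next one, provided it is settled before DOR results are seen. The downside is that the reported median DOR may be slightly shorter.
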